## 4 Population

Subjects that have a history of episodic or chronic cluster headaches (chronic cluster headache subjects not to exceed 50% of total study population) will be included in this study. Subjects enrolled in Cohort 1 will not be allowed to participate in Cohort 2.

### 4.1 Inclusion criteria

1. Subject is male or female age 18-65 inclusive.
2. Written informed consent must be obtained before any assessment is performed.
3. Subjects must have established diagnosis of episodic cluster headaches (CH) or chronic CH, averaging 2-6 headache attacks per day each lasting at least 45 minutes without treatment, not to exceed 6 attacks per day within the last year.
4. Able to communicate well with the investigator, to understand and comply with the requirements of the study, as well as accepting NOT to share any study information through social media during their participation in the study.
5. Subject is able to self-inject medication subcutaneously or have the assistance of a helper on an out-patient basis, if subject is not domiciled in a clinic for the study.

### 4.2 Exclusion criteria

1. Subjects that have a history of greater than 6 CH attacks per day within the last year.
2. Women of child-bearing potential, defined as all women physiologically capable of becoming pregnant, unless they are using highly effective methods of contraception during dosing of study treatment;  
Men who are sexually active with women of child bearing potential, unless they use contraception as specified in [Section 5.1](#) during the study.  
Contraception specific details are listed in [Section 5.1](#).
3. History of multiple and recurring allergies or allergy to the investigational compound/compound class being used in this study.
4. Use of other investigational drugs at the time of enrollment, or within 5 half-lives of enrollment, or within 30 days, whichever is longer; or longer if required by local regulations.
5. A history of clinically significant heart diseases, ECG abnormalities, continued use of drugs known to prolong QTc during the study conduct, or any of the following ECG abnormalities at screening or baseline:
  - QTcF > 450 msec (males)
  - QTcF > 460 msec (females)
6. Uncontrolled diabetes as evidenced by screening HbA1c > 8.0%
7. History of immunodeficiency diseases, including a positive HIV (ELISA and Western blot) test result.
8. A positive Hepatitis B surface antigen or Hepatitis C test result.
9. A positive pregnancy test or lactating mothers.
10. History of drug or alcohol abuse within the 12 months prior to dosing other than prescription medications to manage their CH attacks, or evidence of such abuse as

indicated by the laboratory assays conducted during screening and in the judgment of the Investigator.

11. Significant acute illness which has not resolved within two (2) weeks prior to initial dosing.
12. Any surgical or medical condition which might significantly jeopardize the subject's safety in case of participation in the study. The Investigator should make this determination in consideration of the subject's medical history and/or clinical or laboratory evidence of any of the following:
  - Liver disease or liver injury as indicated by abnormal liver function tests. ALT (SGPT), AST (SGOT),  $\gamma$ -GT, alkaline phosphatase and serum bilirubin will be tested.
    - ALT must be within the normal range
    - Serum bilirubin must not exceed 1.2 x ULN
    - $\gamma$ -GT, AST and alkaline phosphatase must not exceed 2 x ULN
- [If necessary, laboratory testing may be repeated on one occasion (as soon as possible) prior to treatment, to rule out any laboratory error]
13. Acute cholecystitis or symptomatic cholelithiasis in subjects without H/O cholecystectomy

## **5        Restrictions for Study Subjects**

During recruitment, screening/informed consent review, and baseline visit, the subjects must be informed and reminded of the following restrictions:

### **5.1      Contraception requirements**

Female subjects of child-bearing potential must use highly effective methods of contraception during dosing of study treatment. Highly Effective contraception methods include:

- Total abstinence from heterosexual intercourse (when this is in line with the preferred and usual lifestyle of the subject). Periodic abstinence (e.g., calendar, ovulation, symptothermal, post-ovulation methods) and withdrawal are not acceptable methods of contraception.
- Female sterilization (have had surgical bilateral oophorectomy with or without hysterectomy) or tubal ligation at least six weeks before taking study treatment. In case of oophorectomy alone, only when the reproductive status of the woman has been confirmed by follow up hormone level assessment.
- Male sterilization (at least 6 months prior to screening). For female subjects on the study, the vasectomized male partner should be the sole partner for that subject.
- Use of oral, injected or implanted hormonal methods of contraception or other forms of hormonal contraception that have comparable efficacy (failure rate <1%), for example hormone vaginal ring or transdermal hormone contraception or placement of an intrauterine device (IUD) or intrauterine system (IUS).

In case of use of oral contraception women should have been stable on the same pill for a minimum of 3 months before taking study treatment.

Women are considered post-menopausal and not of child bearing potential if they have had 12 months of natural (spontaneous) amenorrhea with an appropriate clinical profile (e.g. age appropriate, history of vasomotor symptoms) or have had surgical bilateral oophorectomy (with or without hysterectomy), total hysterectomy or tubal ligation at least six weeks ago. In the case of oophorectomy alone, only when the reproductive status of the woman has been confirmed by follow up hormone level assessment is she considered not of child bearing potential.

Male contraception is aligned with the local Health Authority requirements i.e. no male contraception in the UK. In the US and Germany, condom contraception for a male subject starts at the Baseline Visit, and until at least 3 days after the last administration of study drug. (3 days equals 5 half-lives of SOM230)

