Key Inclusion criteria	
 
Subject is male or female age 18-65 inclusive.
 
Subjects must have established diagnosis of episodic cluster headaches (CH) or chronic CH, averaging 2-6 headache attacks per day each lasting at least 45 minutes without treatment, not to exceed 6 attacks per day within the last year.
 
Able to communicate well with the investigator, to understand and comply with the requirements of the study, as well as accepting NOT to share any study information through social media during their participation in the study.
 
Subject is able to self-inject medication subcutaneously or have the assistance of a helper if warranted.
 

Key Exclusion criteria	
 
Subjects that have a history of greater than 6 CH attacks per day within the last year.
 
Women of child-bearing potential, defined as all women physiologically capable of becoming pregnant, unless they are using highly effective methods of contraception during the duration of the study. Men who are sexually active with women of child bearing potential, unless the male subjects use condoms during the study as per local requirements.
 
History of multiple and recurring allergies or allergy to the investigational compound/compound class being used in this study.
 
Use of other investigational drugs at the time of enrollment, or within 5 half-lives of enrollment, or within 30 days, whichever is longer; or longer if required by local regulations.
 
A history of clinically significant heart diseases, ECG abnormalities, continued use of drugs known to prolong QTc during the study conduct, or any of the following ECG abnormalities at screening or baseline: 
 
QTcF > 450 msec (males)
 
QTcF > 460 msec (females)
 
 
 
Uncontrolled diabetes as evidenced by screening HbA1c > 8.0%
 
A positive Hepatitis B surface antigen or Hepatitis C test result.
 
Acute cholecystitis or symptomatic cholelithiasis in subjects without H/O cholecystectomy
 

Investigational and reference therapy	
 
SOM230 (pasireotide)
 
Placebo
 

Efficacy/PD assessments	Corporate Confidential Information

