### 3.1    **Study design**

This non-confirmatory study will be conducted in 2 cohorts using a one-sequence two-period design to compare SOM230 vs. Placebo. Following observed efficacy and safety signals in Cohort 1 with the 1.5 mg dose, cohort 2 of the study assessing efficacy of a lower SOM230 dose (0.9 mg) may be considered.

Two consecutive attacks will be treated: first attack will be treated with placebo (Period 1) and the following attack will be treated with SOM230 (Period 2). Approximately 30 patients will be enrolled in Cohort 1 to receive Placebo s.c. single dose in Period 1 then SOM230 1.5 mg s.c., a single dose in Period 2. Each study cohort will consist of a 21 day screening period, a baseline period of 3 days prior to the Baseline Visit, a treatment period (Period 1) lasting up to 3 days then a treatment period 2 of up to 3 days, followed by an end of study visit 3 days after study drug administration in Period 2. The subjects will have up to 5visits. Similarly, in Cohort 2 approximately 30 subjects will receive placebo s.c. single dose in Period 1 and SOM230 0.9 mg s.c., as a single dose in Period 2. Each subject will be instructed to self-administer (or assisted by a helper, or by medical staff if domiciled at a clinic) the study medications at the beginning of the CH attack (as early as possible; within 10 minutes of start of attack when pain is at least moderate). In case patient experiences CH attacks PRIOR to administering study treatment in Period 1 they can use 100% O2 or their conventional treatment to manage their acute attacks experienced before Period 1. If the subject does not have a headache attack in **72 hours post-baseline** or 72 hours post Period 1 treatment the subject will be excluded from the study. Subjects will be required to complete a patient diary to document the pain severity and pain relief before and after the administration of the study medication (**Figure 3-1**). In case the pain is not responding to the administered study drug after 30 minutes, subjects will be allowed to use only 100% oxygen as a rescue

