### 3.6 Risks and benefits

There is no benefit expected for subjects participating in this study.

Based on the knowledge of the somatostatin (SSA) drug class and experience gained during the clinical development of pasireotide, potential risks identified included QT-prolongation, bradycardia, hyperglycemia, cholelithiasis, hematological abnormalities, abnormal liver functions, injection site reactions, gastrointestinal disorders, pancreatitis, and hypothyroidism.

The risk to subjects in this trial will be minimized by adherence to the eligibility criteria, close clinical monitoring, and a single dose study.

Corporate Confidential Information

In patients with cluster headache attacks, because of their severe pain condition hyperactivity of sympathetic system results in tachycardia making the chance of relevant QT prolongation unlikely. Based on the interpretation of the central tendency results of the TQT study the prolonging effect on QT interval associated with pasireotide treatment does not translate into increased pro-arrhythmic risk. The impact of GI AEs on the study outcome is minimal as the endpoint is being determined shortly post-dosing (at 30 minutes), i.e. prior to experiencing this set of AEs. For the LFT elevation, this risk is minimal because of the single dose used in this study. Furthermore, cholelithiasis risk is minimal given the single dose administration and applying the exclusion criteria.

A maximum of 75 mL of blood is planned to be collected over a period of approximately a month, from each subject as part of the study. Additional samples for monitoring of any safety findings would be in addition to this. This is not considered to be a risk for this population. However, injection site reactions and infections at injection site are additional related risks.

Women of child bearing potential should be informed that taking the study drug may involve unknown risks to the fetus if pregnancy were to occur during the study and agree that in order to participate in the study they must adhere to the contraception requirement for the duration of the study and have a negative pregnancy test at the beginning of the study. If there is any question that the subject will not reliably comply, they should not be entered in the study.

There may be unknown risks of SOM230 which may be serious and unforeseen. Subjects will be notified in case any of these unknown risks become identified.

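### Exclusion criterion 2 and Section 5.1 require women's contraception only during dosing, so they leave out the roughly 3 days of SOM230 exposure that follow the last injection

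*Protocol*

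**What the plan says.** The protocol states the contraception period for women of child-bearing potential in four places.

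- Synopsis, key exclusion criteria: such women are excluded "unless they are using highly effective methods of contraception during the duration of the study".
- Section 3.6: to take part, "they must adhere to the contraception requirement for the duration of the study".
- Section 4.2, exclusion criterion 2: such women are excluded "unless they are using highly effective methods of contraception during dosing of study treatment". The criterion refers to Section 5.1 for details.
- Section 5.1: "Female subjects of child-bearing potential must use highly effective methods of contraception during dosing of study treatment".

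Section 5.1 gives a post-dose period only for men. In the US and Germany, condom use runs from the Baseline Visit until at least 3 days after the last administration, with the reason that "3 days equals 5 half-lives of SOM230". For the UK the rule is "no male contraception in the UK".

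Sections 3.1 and 6.2 fix the order of treatment: placebo in Period 1, then one SOM230 dose in Period 2. Footnote 10 to Table 8-1 puts the end of study visit 3 days after the Period 2 dose. The SAP does not address contraception.

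**The concern.** The two shorter statements are in the sections a site works from. Section 4.2 decides eligibility. Section 5 opens by saying that "the subjects must be informed and reminded of the following restrictions", and 5.1 is the first of these. A site that follows 4.2 and its cross-reference to 5.1 finds the same short period in both and no instruction for the time after the last injection.

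Section 3.6 acknowledges that the risk to a fetus is unknown if pregnancy occurs during the study. The days that matter most for that risk are those with SOM230 in the body, and these are the days the shorter wording omits. At stake is subject protection and the consistency of the protocol, not the estimate of efficacy.

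**Working it through.** **Comparison of the four statements.**

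| Place | Period for women | Covers the days after the SOM230 dose? |
|---|---|---|
| Synopsis | Whole study | Yes, to end of study |
| 3.6 | Whole study | Yes, to end of study |
| 4.2, criterion 2 | During dosing | Not stated |
| 5.1 | During dosing | Not stated |

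The periods are nested: contraception for the whole study satisfies all four. The problem is that 4.2 and 5.1 ask for less than the other two.

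**Does a generous reading of dosing close the gap?** Take dosing to mean the whole phase from the first injection to the last.

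1. The first administration is placebo (3.1, 6.2), so there is no SOM230 exposure before Period 2.
2. The only SOM230 administration is in Period 2, and it is the last.
3. The generous span therefore ends where SOM230 exposure starts. None of the exposure after the dose is expressly covered.

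**Size of the uncovered window.** The inputs are 3 days = 5 half-lives (5.1) and the end of study visit 3 days after the Period 2 dose (Table 8-1, footnote 10).

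- Window: 3 × 24 = 72 h, which is the same interval the protocol equates to 5 half-lives.
- Implied half-life: 72 / 5 = 14.4 h.
- Fraction remaining at time *h*, assuming first-order elimination: 2^(−*h*/14.4).
  - 24 h: 2^(−1.667) = 0.315, about 31%.
  - 48 h: 2^(−3.333) = 0.099, about 10%.
  - 72 h: 2^(−5) = 0.031, about 3%.

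The readable text gives no separate half-life, so the equivalence in 5.1 is taken as stated.

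**Comparison with neighbouring rules.** Within criterion 2 itself, men are bound during the study and women only during dosing. Alcohol and strenuous exercise (5.3, 5.4) are restricted until after the study completion evaluation. As written, the alcohol rule lasts longer than the contraception rule for women.

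**Does the end of study visit alone give 3 days?** Not always. Under footnote 2 to Table 8-1, a subject who needs other treatment may be discontinued about 24 hours after dosing, with the end of study evaluations done at that point. On the figures above, about 31% of the drug would remain. A rule tied only to the visit could then end early, so an explicit 3-day minimum is needed as well.

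**The case against.** The strongest reply is that the protocol, read as a whole, already covers these days. Section 3.6 is body text. It makes contraception for the whole study a condition of entry, and it says a woman whose compliance is in doubt should not be entered. On this reading, 5.1 supplies the methods and 3.6 the duration. This stands as evidence of intent. It does not correct 4.2 and 5.1, which state their own, shorter period.

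The second reply is that the listed methods (sterilization, a vasectomized sole partner, intrauterine devices, hormonal methods, abstinence as a usual way of life) are not used only on the day of an injection. A woman would have to stop an established method within 72 hours of one dose. This also stands, and it makes the practical gap small. Abstinence and the pill still depend on the subject continuing them. The urine pregnancy test at end of study (8.4.6) detects a pregnancy but does not prevent exposure.

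Third, the consent pages and the Site Operations Manual are not available here, so what women are actually told cannot be seen. That is correct. The point concerns the protocol text only.

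Fourth, the percentages come from a possibly rounded half-life, ignore absorption from the injection site, and measure residual drug rather than fetal risk. That is fair: they only indicate scale. The UK rule for men follows local requirements and has no bearing on the rule for women.

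**Conclusion.** The concern holds. Criterion 2 and Section 5.1 set a shorter contraception period for women than the synopsis and 3.6, and reading dosing as the whole injection phase does not repair it, because SOM230 is always the last dose. The uncovered window is about 3 days, or 5 half-lives on the protocol's own figure.

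The importance is low. The longer period was plainly intended, most of the methods continue anyway, and no endpoint, sample size or analysis is touched. The 72-hour window rests on the protocol's visit timing. The residual percentages rest additionally on its half-life statement and on first-order elimination.

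**What to change.** Amend Sections 4.2 and 5.1 so that women of child-bearing potential use highly effective contraception for the duration of the study, through the subject's own end of study visit and for at least 3 days (5 half-lives) after the last dose. Put the same wording in the synopsis and Section 3.6 so that all four places agree.

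Name the subject's own visit, because Section 7.2 defines study completion by the last subject's visit. Keep the 3-day minimum for subjects discontinued early.

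The cost is wording in four places. It needs a written amendment with the approvals listed in Section 13.1, and could be included in the next one. No visit, test or analysis changes, and the synopsis and 3.6 already ask for contraception throughout the study.

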## **5.2 Prohibited treatment**

Subjects will not be allowed to take the following at least 24 hours before Baseline Visit through study completion:

- Use of steroids
- Use of ergot compounds, or other prophylactic therapies for cluster headache such as verapamil, or any drug known to cause QTc prolongation or Preventive care for at least 3 half-lives prior to study drug administration
- Use of NSAIDS

## **5.3 Dietary restrictions**

- No alcohol from 24 hours before Baseline Visit until after Study Completion evaluation.

## **5.4 General restrictions**

- No strenuous physical exercise (e.g. weight training, aerobics, football) from 24 hours before Baseline Visit until after Study Completion evaluation (End of Study visit).

# **6 Treatment**

## **6.1 Study treatment**

Details on the storage and management of study medication, treatment and instructions for prescribing and taking study treatment are outlined in Section 3 of the Site Operations Manual.

### **6.1.1 Investigational treatment**

The investigational drug, SOM230 0.6mg, 0.9mg and placebo. will be supplied by Novartis as single blind patient kits. Patients will be instructed on home based administration of study drug, or assisted by a helper/medical staff. Further details will be included in the Site Operations Manual.

### **6.1.2 Additional study treatment**

N/A

## **6.2 Treatment arms**

The number of patients with chronic cluster headache is not to exceed 50% of patients in each cohort. Subjects enrolled in Cohort 1 will not be allowed to participate in Cohort 2.

Study treatments are defined as:

Cohort 1:

- A: single dose of placebo s.c. (Cohort 1-Period 1)
- B: single dose of 1.5 mg s.c. SOM230 (Cohort 1-Period 2)

Subjects will receive both treatments starting with placebo

Cohort 2

- A: single dose of placebo s.c (Cohort 2 – Period 1)
- B: single dose of 0.9 mg s.c. SOM230 (Cohort 2- Period 2)

Subjects will receive both treatments starting with placebo

## **6.3 Permitted dose adjustments and interruptions of study treatment**

Study drug dose adjustments and/or interruptions are not permitted.

## **6.4 Treatment assignment**

This study is a non-randomized study.

## **6.5 Treatment blinding**

This study is a non-randomized and subject blinded study: subjects will remain blinded to the identity of study treatments during the study.

Corporate Confidential Information

## **6.6 Emergency breaking of assigned treatment code**

The investigator will be unblinded, however the subject will remain blinded. There will not be a need for emergency breaking codes at the site for this study.

## **6.7 Treatment exposure and compliance**

Pharmacokinetic parameters (measures of treatment exposure) will be determined in all subjects treated with [SOM230], as detailed in [Section 8.5](#).

## **6.8 Recommended treatment of adverse events**

Medication used to treat AEs must be recorded on the Concomitant medications/Significant non-drug therapies CRF.

## **6.9      Rescue medication**

Subjects will be allowed to use 100% oxygen as rescue medication during the study as described in [Section 7.1](#). If subjects require use of other rescue medication, they must contact the site immediately to be discontinued from the study. Every effort must be made to obtain study data for at least 24 hours after study medication has been administered. Use of rescue medication must be recorded on the Concomitant medications/Significant non-drug therapies CRF after start of study drug.

## **6.10     Concomitant treatment**

Subjects are not to take any other medication to treat cluster headaches other than study medication. Concomitant treatment will be limited to only treat adverse experiences not associated with cluster headaches. Patients will be allowed to take 100% oxygen as rescue medication during the study starting 30 minutes after study drug administration.

In case patient experiences CH attacks PRIOR to administering study treatment in Period 1 they can use 100% O2 or their conventional treatment to manage their headache attacks experienced before Period 1.

